
Summary of Main Exclusion Criteria
	
The participant must be excluded from participating in the trial if the participant:
 
 1. Has extrahepatic metastasis. 2. Systemic anticancer treatment for HCC. 3. Has any contraindication for TACE including portosystemic shunt, hepatofugal blood flow, known severe atheromatosis. 4. Has history of bleeding within the 4 weeks preceding study enrolment. 5. Has hepatic encephalopathy. 6. Has ascites that is refractory to diuretic therapy. 7. Has documented occlusion of the hepatic artery or the main portal vein (segmental portal vein thrombosis does not represent exclusion criterion provided this does not contraindicate TACE).

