4.1.2 Exclusion criteria

The subject must be excluded from participating in the trial if the subject:

1. Has extrahepatic metastasis.
2. systemic anticancer treatment for HCC.
3. Has any contraindication for TACE including portosystemic shunt, hepatofugal blood flow, known severe atheromatosis.
4. Has history of bleeding within the 4 weeks preceding screening.
5. Has hepatic encephalopathy.
6. Has ascites that is refractory to diuretic therapy.
7. Has documented occlusion of the hepatic artery or the main portal vein (segmental portal vein thrombosis does not represent exclusion criterion provided this does not contraindicate TACE).
8. Is currently participating and receiving IMP or has participated in a study of an IMP and received IMP or used an investigational device within 4 weeks of the first dose of IMP.
9. Has a diagnosis of immunodeficiency or is receiving systemic steroid therapy or any other form of immunosuppressive therapy.
10. Has a known history of active TB (Bacillus Tuberculosis)
11. Hypersensitivity to Pembrolizumab or any of its excipients.
12. Has a known additional malignancy that is progressing or requires active treatment. Exceptions include basal cell carcinoma of the skin or squamous cell carcinoma of the skin that has undergone potentially curative therapy or *in situ* cervical cancer.
13. Has active autoimmune disease that has required systemic treatment in the past 2 years (i.e. with use of disease modifying agents, corticosteroids or immunosuppressive drugs). Replacement therapy (eg. thyroxine, insulin, or physiologic corticosteroid replacement therapy for adrenal or pituitary insufficiency, etc.) is not considered a form of systemic treatment.
14. Has known history of, or any evidence of active, non-infectious pneumonitis.
15. Has an active infection requiring systemic therapy. Exceptions relating to Hepatitis B and C virus infection are documented in Section 5.3.1, Table 5.
16. Has a history or current evidence of any condition, therapy, or laboratory abnormality that might confound the results of the trial, interfere with the subject's participation for the full duration of the trial, or is not in the best interest of the participant to participate, in the opinion of the PI.
17. Has known psychiatric or substance abuse disorders that would interfere with cooperation with the requirements of the trial.

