All cases of retreatment and permanent discontinuation must be reported to the Sponsor, CI/delegate and recorded in the eCRF.

a. ALT:

- i. Among participants with Day 1 ALT $<2 \times \text{ULN}$: ALT $\geq 5 \times \text{ULN}$
- ii. Among participants with Day 1 ALT $\geq 2 \times \text{ULN}$: ALT $>3 \times$ the Day 1 level
- iii. ALT $>500 \text{ U/L}$ regardless of baseline level

b. AST:

- i. Among participants with Day 1 AST $<2 \times \text{ULN}$: AST $\geq 5 \times \text{ULN}$
- ii. Among participants with Day 1 AST $\geq 2 \times \text{ULN}$: AST $>3 \times$ the Day 1 level
- iii. AST $>500 \text{ U/L}$ regardless of baseline level

c. Total Bilirubin:

- i. Among participants with baseline levels $<25.65 \text{ } \mu\text{mol/L}$: a value of $>34.2 \text{ } \mu\text{mol/L}$.
- ii. Among participants with baseline levels that are $\geq 25.65 \text{ } \mu\text{mol/L}$: a value $\geq 2 \times$ the baseline level
- iii. Total bilirubin $>51.3 \text{ } \mu\text{mol/L}$ regardless of baseline level

d. Regardless of laboratory values, hepatic decompensation diagnosed clinically, including:

- i. New onset clinically detectable ascites
- ii. Gastrointestinal bleeding suggestive of portal hypertension (e.g., esophageal or gastric varices)
- iii. Encephalopathy

(Participants with clinically apparent ascites or encephalopathy, or untreated varices are not eligible for enrolment)

Immediate assessment

All participants

- All participants should be evaluated according to directions below within 72 hours of alert for non-overdose ECI
- Procedures:
 - Obtain a consultation with a hepatologist

- Obtain a work-up for hepatitis if there is no underlying hepatitis, including hepatitis A, B,C, D, E, Epstein-Barr virus, and cytomegalovirus
- Assess for ingestion of drugs/supplements with hepatotoxic potential
- Assess for alcohol ingestion
- Assess for potential bacterial infection, biliary obstruction, or occult gastrointestinal bleeding
- Repeat ALT, AST, Tbil, Dbil, ALP, γ -glutamyl transpeptidase (GGT), INR, and FBC with differential
- Other laboratories or imaging studies as clinically indicated
- Consider liver biopsy if indicated by hepatologist

Hepatitis C-Infected Subjects (including subjects who previously achieved SVR 12)

- In addition to the above, measure HCV RNA viral load

Hepatitis B-infected Subjects

- HBV DNA, HBsAg, HBeAg, HBCT (anti-HBV core total IgG/IgM), HBeAb (anti-HBV antibody), HBSab (anti-HBV Surface Antibody)

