- Participants should be questioned about compliance with the use of anti-viral agents.

Permanent Discontinuation Criteria for Subjects with Non-overdose Hepatic ECIs

Therapy should also be permanently discontinued for any of the following:

- ALT >20 \times ULN
- Child-Pugh score of ≥ 9 points
- Gastrointestinal bleeding suggestive of portal hypertension (e.g., esophageal or gastric varices)
- New onset clinically detectable ascites
- Encephalopathy
- Recurrence of a severe or life-threatening event, or of any of the laboratory abnormalities listed above, that are presumed to be immune-related.

Other participants may be eligible for treatment interruption (and potential re-start) of Pembrolizumab after discussion with the Sponsor, CI/delegate.

Diagnosis and Management of Non-Overdose Hepatic ECIs

HCC subjects are at risk for a range of complications that can cause hepatic laboratory abnormalities with or without clinical decompensation. Those with a history of chronic HCV or HBV infection also have the potential to experience virologic flares. Immune-related hepatitis has been observed in $\sim 1\%$ of subjects who received Pembrolizumab. The following section provides further guidance on the diagnosis and management of potential hepatic complications among HCC subjects.

a. Hepatitis B Flare

Hepatitis B flares are characterized by rapid elevations of ALT and AST to $>5\times$ ULN and/or $>3\times$ baseline. ALT elevation to $\geq 10\times$ ULN is common. In the absence of hepatic decompensation, ALT/AST elevations are typically isolated (i.e. limited/no elevations of bilirubin/ALP). Participants who are compliant with anti-viral therapy should have continued suppression of HBV DNA at the time of flare; thus, detection of HBV DNA should prompt questioning of subjects for compliance. Laboratory abnormalities secondary to flare are typically observed for 3-5 weeks.

Among participants with HBV, a flare should be considered if this pattern is observed and there is no evidence of an alternative etiology. Guidelines for participants with a diagnosis of HBV flare are as follows:

- Care should be instituted in consultation with a hepatologist.
- For participants who have detectable HBV DNA, re-institute anti-viral therapy.

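### Section 6.8.3 treats apparent ascites and untreated varices as bars to entry, but the exclusion lists bar only diuretic-refractory ascites and never mention varices

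*Combined protocol and SAP*

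**What the plan says.** Section 6.8.3 of the Combined protocol and SAP lists the hepatic events of clinical interest (ECIs). Item d covers clinically diagnosed hepatic decompensation, with ascites, portal-hypertensive bleeding and encephalopathy listed under it. Directly after that list stands the sentence "Participants with clinically apparent ascites or encephalopathy, or untreated varices are not eligible for enrolment".

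Section 4.1.2 sets the exclusion criteria. On the three conditions named in 6.8.3 it says:

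- Ascites (exclusion 6): "Has ascites that is refractory to diuretic therapy". The Trial Summary has the same wording.
- Encephalopathy (exclusion 5): "Has hepatic encephalopathy".
- Varices: not named in either list. The nearest item is exclusion 4, "Has history of bleeding within the 4 weeks preceding screening" (in the Trial Summary, "Has history of bleeding within the 4 weeks preceding study enrolment").

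Further on in 6.8.3, the permanent-discontinuation list for hepatic ECIs includes "New onset clinically detectable ascites", portal-hypertensive gastrointestinal bleeding, encephalopathy and a Child-Pugh score of 9 or more.

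**The concern.** Section 5.1.1.2 has the investigator confirm eligibility against the inclusion and exclusion criteria, which are in Section 4.1. The restriction in 6.8.3 sits in parentheses inside on-treatment event guidance and is worded as if it reported a rule set elsewhere. No such rule appears in the lists. A site working from 4.1.2 and a site that has also read 6.8.3 could reach opposite decisions on the same patient, and the trial may run at up to four sites.

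This is a liver-safety trial. Part 1 has six participants, at least one of whom must be Child-Pugh B7, and Section 3.1.1 directs the monitoring committee's attention to acute liver toxicity. Who may enter with existing signs of portal hypertension affects both participant safety and how hepatic events in so small a group are read. It also affects whether an event defined as new onset can be applied to everyone enrolled.

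**Working it through.** The plan states no figure on this point and no formula applies. The check sets the texts side by side.

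| Condition barred in 6.8.3 | Trial Summary and 4.1.2 | Match? |
|---|---|---|
| Encephalopathy | Exclusion 5 bars it | Yes |
| Clinically apparent ascites | Exclusion 6 bars only refractory ascites | No: the lists are narrower |
| Untreated varices | Not named | No: absent |

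**Step 1. Does another criterion supply the missing bar?**

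- Exclusion 3, "Has any contraindication for TACE including portosystemic shunt, hepatofugal blood flow, known severe atheromatosis", names neither ascites nor varices.
- Exclusion 4 concerns recent bleeding. Varices that have not bled fall outside it.
- Exclusion 16, "Has a history or current evidence of any condition, therapy, or laboratory abnormality that might confound the results of the trial", depends on the investigator's opinion. It permits exclusion but does not impose the categorical bar that 6.8.3 asserts.
- The Child-Pugh limit of 7 is a total score. The protocol gives no component table and no separate ascites condition, so the documents do not show that the limit removes apparent ascites.
- The Time & Events table, as extracted, lists Child-Pugh assessment and a physical examination at screening, but no endoscopy or other named check for varices.

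None of these closes the gap. Because exclusion 6 names refractory ascites specifically, it implies that other ascites may enter.

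**Step 2. Which patients are in conflict?**

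- Refractory ascites that is clinically apparent: barred by both texts.
- Ascites controlled so that it is no longer apparent: barred by neither.
- Ascites that is apparent but not refractory: enrollable under the lists, barred under 6.8.3.
- Treated varices: barred by neither.
- Untreated varices: enrollable under the lists, barred under 6.8.3.

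The conflict is confined to the third and fifth groups.

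**Step 3. What follows for the stop rule?** For a participant who enters with apparent ascites that later worsens, the ascites item in the discontinuation list does not clearly apply, because it is limited to new onset. By contrast, the ALT, AST and bilirubin criteria in 6.8.3 are set relative to the Day 1 or baseline value. Other provisions still apply: Section 7.1 makes clinically significant worsening of a pre-existing condition an adverse event, and Child-Pugh is reassessed at treatment-cycle visits, with 9 or more as a stop criterion.

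**The case against.** The strongest reply is that little is lost in practice, and several parts of it stand.

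- A reader might infer that decompensation would be under-counted in the primary outcome. The documents do not support this. The primary endpoint is adverse events graded by CTCAE, and worsening of baseline ascites is captured under Section 7.1. Item d in 6.8.3 is also open-ended: it introduces its examples with the word including, so worsening ascites diagnosed as decompensation can still be reported as an ECI.
- A reader might infer that bleeding from pre-existing varices would distort the ECI count. That does not follow either. The ECI is the bleed and is not limited to new onset. Participants with treated varices may enter under both texts. Section 7.5 has ECIs reported regardless of relationship to the drug, and causality is rated separately for each adverse event under Section 7.2.1.2.
- Exclusions 3 and 16 and the Child-Pugh limit give investigators grounds to screen out some of these patients, so it cannot be said that the 6.8.3 restriction would never be applied.

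The reply does not remove the contradiction. Discretionary grounds are not the categorical bar stated in 6.8.3, and the event-capture provisions do not settle who may be enrolled.

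**Conclusion.** The point holds as an internal inconsistency in the eligibility text. Of the three conditions that 6.8.3 calls ineligible, one agrees with the exclusion lists, one is narrower there and one is missing. Following the plan as written gives two entry rules for patients with apparent, non-refractory ascites or with untreated varices. It also leaves one item of the permanent-discontinuation list unclear for anyone admitted with apparent ascites.

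The size cannot be put in numbers: the documents give no prevalence for either condition in this population, and the conclusion does not need one. No sample-size, precision or error-rate figure is affected, and recording of adverse events for the primary endpoint remains intact. The point merits correction because it bears on who is enrolled and on participant safety in a trial whose run-in has six participants. It rests only on the current text of the Trial Summary and Sections 4.1.1, 4.1.2 and 6.8.3.

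**What to change.** Reconcile the Trial Summary, Section 4.1.2 and the parenthetical in Section 6.8.3 so that one eligibility statement for ascites and varices applies at all sites. Then check that the ascites wording in the 6.8.3 event list and permanent-discontinuation list is consistent with the population chosen. Which clinical rule to adopt, for entry and for stopping, is the sponsor's decision. Hepatic ECIs require treatment to be held, so any change to that wording is a clinical matter as well as an editorial one.

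The cost is a wording amendment. Depending on the rule chosen, the screening pool would be confirmed as it stands or somewhat narrowed. The statistical analysis does not change.

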4.1.1 Inclusion criteria

In order to be eligible for participation in this trial, the participant must:

1. Be willing and able to provide written informed consent/assent for the trial.
2. Be ≥ 18 years of age on day of signing informed consent.
3. Have a diagnosis of Hepatocellular Cancer (HCC) based on AASLD criteria (Appendix 1).
4. Have at least one uni-dimensional lesion measurable by CT-scan or MRI based on mRECIST criteria.

5. Patients who received prior TACE treatment (conventional or DEB-TACE) are eligible, provided they have at least one previously untreated lesion that is measurable based on mRECIST criteria.
6. Be ineligible for surgical resection or liver transplantation. Have a performance status of 0 or 1 on the ECOG Performance Scale (Appendix 2).
7. Demonstrate adequate organ function as defined in the table below.

System	Laboratory Value
Haematological	
Absolute neutrophil count (ANC)	$\geq 1,500 \text{ mcL}$
Platelets	$\geq 60,000 \text{ mcL}$
Haemoglobin	$\geq 9 \text{ g/dL}$ or $\geq 5.6 \text{ mmol/L}$ without transfusion or Erythropoietin (EPO) dependency
Renal	
Serum creatinine OR Measured or calculated ^a creatinine clearance (CrCl) calculated by Cockcroft Gault criteria [Glomerular Filtration Rate (GFR) can also be used in place of creatinine or CrCl]	$\leq 1.5 \times \text{upper limit of normal (ULN)}$ OR $\geq 60 \text{ mL/min}$ for subject with creatinine levels $> 1.5 \times \text{ULN}$
Hepatic	
Serum total bilirubin	$\leq 3 \times \text{ULN}$ (level of normality $< 21 \text{ } \mu\text{mol/L}$)
AST and ALT	$\leq 5 \times \text{ULN}$
Albumin	$\geq 2.5 \text{ mg/dL}$
Coagulation	
International Normalized Ratio (INR) or Prothrombin Time (PT)	$\leq 1.5 \times \text{ULN}$ unless participant is receiving anticoagulant therapy as long as PT or PTT is within therapeutic range of intended use of anticoagulants
Activated Partial Thromboplastin Time (aPTT)	$\leq 1.5 \times \text{ULN}$ unless participant is receiving anticoagulant therapy as long as PT or PTT is within therapeutic range of intended use of anticoagulants

^aCrCl should be calculated per institutional standard.

Table 2 Adequate Organ Function Laboratory Values

8. Have an overall Child-Pugh score ≤ 7
9. Female subject of childbearing potential should have a negative urine or serum pregnancy. If the urine test is positive or cannot be confirmed as negative, a serum pregnancy test will be required.

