6.6 Dose Modifications for Toxicity

Adverse events (both non-serious and serious) associated with Pembrolizumab exposure may represent an immunologic etiology. These AEs may occur shortly after the first dose or several months after the last dose. Pembrolizumab must be withheld for drug-related toxicities and severe or life-threatening AEs as per Table 8 below. See Section 6.8 for supportive care guidelines, including use of corticosteroids.

Treatment discontinuation for AST, ALT deterioration in participants who present with Grade 2 AST or ALT will be triggered only if AST or ALT increases by greater than or equal to 50% relative to the measurement taken at initiation of systemic treatment (Cycle 1 Day 1) and lasts for at least 1 week.

Toxicity	Hold Treatment For Grade	Timing for Restarting Treatment	Treatment Discontinuation
Diarrhoea/ Colitis	2-3	Toxicity resolves to Grade 0-1	Toxicity does not resolve within 12 weeks of last dose or inability to reduce corticosteroid to 10 mg or less of prednisone or equivalent per day within 12 weeks
	4	Permanently discontinue	Permanently discontinue
AST, ALT, or Increased Bilirubin	2	Toxicity resolves to Grade 0-1	Toxicity does not resolve within 12 weeks of last dose
	3-4	Permanently discontinue (see exception below) ^a	Permanently discontinue
Type 1 diabetes mellitus (if new onset) or Hyperglycaemia	T1DM or 3-4	Hold Pembrolizumab for new onset Type 1 diabetes mellitus or Grade 3-4 hyperglycemia associated with evidence of beta cell failure	Resume Pembrolizumab when participants are clinically and metabolically stable
Hypophysitis	2-4	Toxicity resolves to Grade 0-1. Therapy with Pembrolizumab can be continued while endocrine replacement therapy is instituted	Toxicity does not resolve within 12 weeks of last dose or inability to reduce corticosteroid to 10 mg or less of prednisone or equivalent per day within 12 weeks
Hyperthyroidism	3	Toxicity resolves to Grade 0-1	Toxicity does not resolve within 12 weeks of last dose or inability to reduce corticosteroid to 10 mg or less of prednisone or equivalent per day within 12 weeks
	4	Permanently discontinue	Permanently discontinue
Hypothyroidism		Therapy with Pembrolizumab can be continued while thyroid replacement therapy is instituted	Therapy with Pembrolizumab can be continued while thyroid replacement therapy is instituted

Toxicity	Hold Treatment For Grade	Timing for Restarting Treatment	Treatment Discontinuation

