- If the participant is clinically stable, Pembrolizumab dosing may be interrupted for up to 12 weeks. Subjects should undergo weekly laboratory tests including: AST, ALT, ALP, Tbil, Dbil, INR, HBsAg, HBV DNA (if detected at the onset of the flare). Obtain anti-HBe, anti-HBs, and HBV DNA levels (if not detected at the onset of the flare) every 2-3 weeks.
- If ALT returns to normal or Grade 1 (if normal at baseline), or to baseline grade (if Grade 2 at baseline) within 12 weeks, and participants are clinically stable, participants may restart Pembrolizumab treatment. If these conditions are not met, then Pembrolizumab treatment should be permanently discontinued.

b. Hepatitis C Recurrence or Flare

Participants who achieved a sustained virologic response at 12 weeks on specific antiviral treatment (SVR 12) and subjects with on-going HCV infection are eligible for enrolment. In rare circumstances, HCV participants who achieve SVR 12 may relapse at later time points. Relapse is characterised by detection of HCV RNA, often accompanied by ALT elevations to $>5\times\text{ULN}$. In the absence of hepatic decompensation, ALT/AST elevations are typically isolated (i.e., limited/no elevations of bilirubin/ALP).

Among participants with uncontrolled hepatitis C, virologic flares are possible. Hepatitis C flares are characterized by rapid elevations of ALT and AST to $>5\times\text{ULN}$ and/or $>3\times$ baseline along with a rise in HCV RNA. ALT elevation to $\geq 10\times\text{ULN}$ and a 1 log elevation in HCV RNA level are common. In the absence of hepatic decompensation, ALT/AST elevations are typically isolated (i.e., limited/no elevations of bilirubin/ALP). Laboratory abnormalities secondary to flare or recurrence are typically observed for 3-5 weeks.

Guidelines for participants with recurrent HCV infection or an HCV flare are described below:

i. Recurrent HCV infection:

If the participant entered the study with an HCV RNA test of “Target not Detected” and has confirmed detectable HCV RNA (2 specimens, 1 week apart), then the subject has experienced a late HCV relapse or a recurrent infection.

- Question the participant about use of injection or inhalation drugs
- At the time of first detection of HCV RNA, send a specimen for HCV genotyping
- Measure AST, ALT, ALP, Tbil, Dbil, and INR weekly
- Measure HCV RNA levels every 2 weeks
- Therapy with HCV anti-viral treatments should be strongly considered.

ii. HCV Flare:

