- At the time of first detection of HCV RNA, send a specimen for HCV genotyping
- Measure AST, ALT, ALP, Tbil, Dbil, INR weekly
- Measure HCV RNA levels every 2 weeks
- Therapy with HCV anti-viral treatments should be strongly considered.

iii. For both recurrent infection and HCV flare: if ALT returns to normal or Grade 1 (if normal at baseline), or to baseline grade (if Grade 2 at baseline) within 12 weeks, and the participants are clinically stable, participants may restart Pembrolizumab treatment. If these conditions are not met, then Pembrolizumab treatment should be permanently discontinued.

c. Immune-related hepatitis

i. Description: Immune-related hepatitis due to Pembrolizumab should be suspected if any of the following is seen:

- AST or ALT baseline values are less than 2×ULN, and AST or ALT laboratory values increase to $\geq 5\times$ ULN
- Among participants with Day 1 ALT or AST $\geq 2\times$ ULN, levels increase to $>3\times$ the Day 1 level
- AST/ALT >500 U/L regardless of baseline level
- Among participants with Day 1 Tbil levels <1.5 mg/dL: a value of >2.0 mg/dL
- Among participants with Day 1 Tbil levels that are ≥ 1.5 mg/dL: a value of $\geq 2\times$ the Day 1 level
- Total bilirubin >51.3 μ mol/L regardless of baseline level.

Immune-related hepatitis is a diagnosis made after excluding other possible etiologies for the change. Viral flare (if applicable), biliary or vascular obstruction, infection, medications, and alcohol use must be ruled out (see below).

ii. Management

- Interrupt Pembrolizumab treatment and alert the sponsor/CI or delegate as per ECI criteria above for ALT, AST, bilirubin, and hepatic decompensation.
- Start IV corticosteroid (methylprednisolone 125 mg) followed by oral corticosteroid (1-2 mg/kg/day).
- Monitor with biweekly laboratory tests including AST, ALT, Tbil, Dbil, ALP, and INR.
- If symptoms and laboratory tests resolve to Grade ≤ 1 or baseline (if abnormal at baseline), taper steroids over 28 days. Pembrolizumab treatment may be restarted after steroid treatment has been tapered to prednisone ≤ 10 mg/day (or equivalent dose of another agent). Treatment and laboratory results must be documented.

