- If laboratory abnormalities do not resolve within 3 weeks, or steroids cannot be lowered to ≤ 10 mg/day (or prednisone equivalent) within 12 weeks, or participants show evidence of decompensation to Child-Pugh C status or have esophageal or variceal bleeding at any point, treatment must be permanently discontinued. This must be documented.

d. Other Hepatic Events of Clinical Interest

- Infection needs to be ruled out with cultures of blood, urine, and ascites (if possible), as well as chest x-ray and abdominal imaging if relevant. If an infection is found, antibiotics should be started.
- If Tbil is elevated above baseline, magnetic resonance cholangiopancreatography or ultrasound with doppler should be obtained to rule out vascular compromise, biliary obstruction, and/or tumour progression. If biliary obstruction is present, consultation with a gastroenterologist and/or an interventional radiologist should be obtained to see if the obstruction may be relieved.
- A careful review of drugs, including herbal and alternative medications, should be obtained, and alcohol use should be ruled out.

- For all of these cases, participants may resume Pembrolizumab treatment if they are clinically stable after appropriate therapy or discontinue the causative agent, as long as laboratory values have returned to Grade 1 or baseline (if normal or Grade 1 at start) or to baseline grade within 3 weeks.
- Treatment must be permanently discontinued if the participant is off Pembrolizumab therapy for infection, obstruction, or drug/alcohol-related toxicity for more than 3 weeks, or if they have oesophageal bleeding, or become Child-Pugh C at any point.

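### The restart rules after a hepatitis B or C flare omit a Grade 1 ALT baseline; read literally, a Grade 1 starter who is back at Grade 1 is stopped for good

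*Combined protocol and SAP*

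**What the plan says.** Section 6.8.3 of the protocol gives four sets of management rules for hepatic events of clinical interest.

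- **(a) Hepatitis B flare.** Treatment may restart under this condition, provided the participant is clinically stable: "If ALT returns to normal or Grade 1 (if normal at baseline), or to baseline grade (if Grade 2 at baseline) within 12 weeks". The default follows at once: "If these conditions are not met, then Pembrolizumab treatment should be permanently discontinued".
- **(b.iii) Hepatitis C recurrence or flare.** The condition and the default are the same as in (a).
- **(c) Immune-related hepatitis.** Recovery means resolution to Grade 1 or below "or baseline (if abnormal at baseline), taper steroids over 28 days". Restart may follow once steroids are down to 10 mg/day of prednisone or equivalent.
- **(d) Other hepatic events.** A stable participant may resume on this condition: "laboratory values have returned to Grade 1 or baseline (if normal or Grade 1 at start) or to baseline grade within 3 weeks".

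On who can start with a raised ALT, section 4.1.1 item 7 requires participants to "Demonstrate adequate organ function as defined in the table below", and that table (Table 2) admits AST and ALT up to 5 x ULN. Section 6.6 and footnote a of Table 8 make explicit provision for participants who are at Grade 2 AST or ALT on Cycle 1 Day 1.

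**The concern.** Rules (a) and (b.iii) name two baselines, normal and Grade 2, and skip the one between them. Because each rule ends in a default of permanent discontinuation, the omission has a stated consequence: the unnamed participant falls into the default.

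The resulting order makes no clinical sense. Someone who began normal and ends at Grade 1, worse than at the start, may restart. Someone who began and ends at Grade 2 may restart. Someone who began at Grade 1 and has returned fully to Grade 1, no worse than the first and better than the second, should be stopped for good. The protocol gives no reason for this.

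At stake is the loss of study treatment by a recovered participant, or different handling of the same case across up to four sites. Section 8.3 summarises adverse events by their impact on the study drug, so such a stop would also appear in the primary tolerability summary.

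**Working it through.** There is no planned figure to reproduce. The check is to list the cases. It needs only that Grade 1 lies between normal and Grade 2; the CTCAE cut-offs, which the documents do not print, are not used.

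**Step 1: the two readings.** The bracket limiting the first branch to a normal baseline can attach to Grade 1 alone (reading A) or to both normal and Grade 1 (reading B).

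**Step 2: apply the text.** The participant is taken to be clinically stable, within 12 weeks, and free of the separate permanent-stop criteria in 6.8.3. The last column is the wording proposed under the fix.

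| Baseline ALT | ALT within 12 weeks | Reading A | Reading B | Proposed |
|---|---|---|---|---|
| Normal | Normal | restart | restart | restart |
| Normal | Grade 1 | restart | restart | restart |
| Normal | Grade 2 | stop | stop | stop |
| Grade 1 | Normal | restart | stop | restart |
| **Grade 1** | **Grade 1** | **stop** | **stop** | **restart** |
| Grade 1 | Grade 2 | stop | stop | stop |
| Grade 2 | Normal | restart | stop | restart |
| Grade 2 | Grade 1 | stop | stop | restart |
| Grade 2 | Grade 2 | restart | restart | restart |

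**Step 3: isolate the defect.** Three other cells are less clear. Grade 1 to normal depends on the reading. Grade 2 to normal and Grade 2 to Grade 1 could be read charitably as having returned to baseline grade. None of the three is claimed as the error. Grade 1 to Grade 1 is different: the ALT is not normal, the baseline was not normal, and the baseline was not Grade 2. No branch is met on either reading.

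**Step 4: can the case arise?** Table 2 allows a raised ALT at screening, and Table 8 footnote a foresees Grade 2 on Cycle 1 Day 1, so the milder Grade 1 start is possible. Treated chronic hepatitis B (section 5.2.1, Table 5) and ongoing hepatitis C (section 6.8.3) are both eligible, and 6.8.3 acknowledges that such participants may flare.

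**Step 5: compare the neighbouring rules.** The same Grade 1 starter back at Grade 1 passes rule (c) twice over, being at Grade 1 and at an abnormal baseline. The participant also passes rule (d), which names a Grade 1 start. The omission is confined to the two viral rules.

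**The case against.** The strongest reply concerns force and frequency. Section 6.8.3 presents these rules as guidance, and the default in (a) and (b.iii) is phrased with should, where (c) and (d) use must. Earlier in the section a general clause lets participants outside the listed permanent stops be considered for interruption and possible restart after discussion with the sponsor and chief investigator. Every hepatic event of this kind triggers notification within 24 hours and a hepatology consultation, and every permanent discontinuation is reported. A sensible clinician would probably treat a return to the starting grade as recovery.

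The case is also likely to be rare. Table 5 requires at least 12 weeks of antiviral treatment in chronic hepatitis B and excludes uncontrolled viral load or a flare in that time. Section 1.3.2 cites no flares in preliminary data on another anti-PD-1 antibody, and none among 20 participants with hepatitis C-related HCC given a CTLA-4 inhibitor.

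All of this stands, and it is why the point is minor. It does not close the gap: the general clause states no exception to the specific default, so restarting this participant means departing from the written instruction.

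One further objection is accepted. Table 8 restarts treatment when "Toxicity resolves to Grade 0-1", but that cell covers Grade 2 drug-related liver abnormalities, and the next line of the row stops treatment at Grade 3-4 apart from the footnote. It is weak evidence of what was meant for viral flares. The inference of a slip rests on rules (c) and (d), which cover other diagnoses and so show likely intent without repairing (a) or (b.iii).

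**Conclusion.** The concern holds as a minor drafting error. On either reading, rules (a) and (b.iii) direct permanent discontinuation of a stable Grade 1 starter whose ALT is back at Grade 1 within 12 weeks.

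The number affected cannot be estimated. A participant must have viral hepatitis, start at Grade 1 ALT, have a flare or recurrence, return to Grade 1 in time, be stable, and meet no other stop; the documents give none of these shares. The ceiling is 32 evaluable participants. As a scale only, one such stop would add 1/32 = 3.1 percentage points to a discontinuation proportion with that denominator.

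The error is on the cautious side and exposes nobody to extra drug. Sample size, error rates and analysis methods are unaffected. The conclusion assumes the text is applied as written; central oversight would probably catch the case in practice.

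**What to change.** In 6.8.3 (a) and (b.iii), replace the ALT condition with:

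> If ALT returns to Grade 1 or below, or to baseline grade if Grade 2 at baseline (baseline = Cycle 1 Day 1), within 12 weeks

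The clinical-stability requirement and the discontinuation default stay as they are. The wording covers the Grade 1 baseline, removes the ambiguity over the bracket, and gives a Grade 2 starter who improves below Grade 2 a clear branch. A normal or Grade 1 starter left at Grade 2 still may not restart. Cycle 1 Day 1 is already the reference for AST and ALT change in section 6.6.

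The cost is one condition reworded in two places at the next amendment, with no change to design, sample size or analysis.
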